### **Grouped terms**

In order to most accurately characterize those AEs related to different mechanism, MedDRA SMQ and HLT (with some modification) will be used to group MedDRA PT for

- rash/acne,
- stomatitis,
- paronychia.

As a first step in the analysis of grouped AE, all constituent PT will be presented in a separate table for each grouped AE. Standard tables will be supplemented with tables using the grouped AE.

Groupings will follow the project standard and details are defined in the technical TSAP. In these tables the grouped AEs will replace the original PTs for all AEs that are included within the grouped term. The grouped AE categories will then be tabulated along with all remaining MedDRA PTs, sorted by descending frequency. A reference table presenting all project defined groupings and MedDRA PTs within each grouping will also be produced. The following tables with grouping terms will be provided:

- AEs by treatment, highest CTCAE, using grouped terms and PT
- Drug-related AEs by treatment, highest CTCAE, using grouped terms and PT
- AEs leading to dose reduction by treatment, using grouped terms and PT
- AEs leading to treatment discontinuation by treatment, using grouped terms and PT
- AEs leading to death by treatment, using grouped terms and PT
- SAEs by treatment, highest CTCAE, using grouped terms and PT
- Drug-related SAEs by treatment, highest CTCAE, using grouped terms and PT

Additional tables will be produced to describe the frequency, intensity, time to onset, and clinical consequences for

- diarrhea,
- rash/acne.
- stomatitis

### **Pre-defined adverse events of special interest**

Some pre-defined AEs are considered to be of special interest (AESIs).

Separate listings will be prepared for patients who are identified as having experienced any of the following AEs. Identification will be based upon modified MedDRA SMQ and HLT groupings. If sufficient events occur within the trial, analyses similar to those for diarrhea rash/acne and stomatitis may be performed.

- Diarrhoea
- Rash/ acne
- stomatitis
- Dehydration

- Renal insufficiency
- hepatic impairment
- Interstitial Lung Disease (ILD-like events)
- heart failure
- Keratitis
- Pancreatitis
- Severe cutaneous adverse reactions (Severe skin reaction)
- Gastrointestinal perforation
- Hypersensitivity reaction
- Developmental toxicity

### **Other significant AEs**

Other significant AEs are defined as serious and non-serious AEs that lead to dose reduction or permanent discontinuation of study medication. Their incidence will be reported by severity according to CTCAE grades. A listing of patients who developed ‘other significant’ AEs will be provided and a flag for serious and non-serious will be included.

### **7.8.2 Laboratory data**

The analyses of laboratory data will be descriptive in nature and will be based on BI standards (6). CTCAE version 4.03 grades will be applied to laboratory parameters using the current BI oncology standard as detailed in the document ‘Conversion of laboratory parameters to CTCAE grades within BI’ (5).

Primary laboratory tests are defined as:

- Low values (-): Red blood cell count (RBC), haemoglobin, total white blood cell (WBC), platelets, neutrophils (only at baseline), lymphocytes, sodium, potassium, calcium, and glomerular filtration rate (GFR)

High values (+): aspartate aminotransferase (AST), alanine aminotransferase (ALT), alkaline phosphatase, activated partial thromboplastin time (aPTT), international normalized ratio (INR), creatinine total bilirubin, LDH, uric acid

The following analyses will be presented for the primary laboratory tests:

- Descriptive statistics at each planned assessment
- Frequency of patients with transitions in CTCAE grade from baseline to worst and last values during treatment
- Frequency of patients with possible clinically significant abnormalities.

Possible clinically significant abnormalities are defined as CTCAE grade of 2 or greater, with an increase of at least one grade from baseline.

Frequency and time of onset of liver enzyme elevations will be tabulated. Additional, more in-depth analyses will be performed as needed. These analyses will examine the influence of extent of exposure and time to event onset.

Note: Section 5.3.3 in protocol has detailed list of lab parameters which will be summarized beside important lab parameter mentioned above.

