5.3.3 Safety laboratory parameters

Safety lab will be performed locally at each participating site. Following parameters should be evaluated at each timepoint:

Table 5.3.3: 1 Safety laboratory parameters

Category	Parameters
Hematology	Red blood cell count (RBC), haemoglobin, haematocrit, platelet count, white blood cell count (WBC), with differential (neutrophils, lymphocytes, monocytes, eosinophils, basophils)
Coagulation	International Normalized Ratio (INR), activated Partial Thromboplastin Time (aPTT), Fibrinogen.
Chemistry	
Electrolytes	Sodium, potassium, calcium, magnesium, chloride, bicarbonate (HCO ₃)
Liver function tests	alkaline phosphatase, aspartate aminotransferase (AST), alanine aminotransferase (ALT), γ - glutamyltransferase (GGT), total bilirubin
Renal function parameters	Blood urea/blood urea nitrogen (BUN), creatinine; Creatinine clearance (see Appendix 10.2).
Other	glucose, albumin, cholesterol, triglycerides, phosphorus, lactate dehydrogenase (LDH), total protein, uric acid, creatine phosphokinase (CPK); in case of pathological CPK further evaluation (e.g by determination of isoenzymes, troponin assays, ECG exam) should be performed as clinically indicated
Urinalysis	pH, protein, glucose, ketones, blood, leucocytes, nitrite; in case of pathological finding further evaluation should be performed and results documented. Proteinuria per se will only result in treatment interruptions if associated to other renal pathology which would qualify for treatment interruption i.e. CTCAE \geq 3 AE, or decrease in renal clearance to $<$ 45 ml/min GFR
Pregnancy test	β -HCG testing in urine or serum in women of childbearing potential (WOCBP)

The investigator should complete additional evaluations of laboratory tests as clinically indicated.

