7.3.4 Safety analyses

All patients who receive at least one dose of trial medication will be included in the safety analysis. Adverse events will be graded according to CTCAE, Version 4.03.

Adverse events will be coded using the Medical Dictionary for Regulatory Activities (MedDRA) coding dictionary. Standard BI summary tables and listings will be produced. All adverse events with an onset between start of treatment and end of the residual effect period (REP), a period of 30 days after the last dose of trial medication, will be assigned to the treatment period for evaluation.

Standard tabulations arranged by MedDRA SOC and PT will include:

- The overall incidence and intensity of adverse events,
- AE judged to have been related to afatinib
- AE leading to dosage reduction
- AE leading to permanent treatment discontinuation
- SAE
- Fatal outcome

These standard tables will be supplemented with tables in which MedDRA SMQ and HLT (with some modifications) will be used to group MedDRA PT for the following:

- rash/acne
- stomatitis
- paronychia

Tables that describe the frequency, intensity, time to onset, and clinical consequences will be produced for the following AEs of special interest:

- diarrhea
- rash/acne
- stomatitis

Listings will be prepared of patients who are identified as having experienced any of the following AE. For AE other than dehydration, identification will be based upon modified MedDRA SMQ and HLT groupings.

- Dehydration
- Renal insufficiency
- hepatic impairment
- ILD-like events
- heart failure
- Keratitis
- Pancreatitis
- Severe skin reaction
- Gastrointestinal perforation
- Hypersensitivity reaction
- Developmental toxicity

Primary laboratory tests are defined as:

- Low values (-): haemoglobin, total WBC, platelets, neutrophils, lymphocytes, potassium, magnesium, sodium, creatinine clearance and GFR
- High values (+): AST, ALT, alkaline phosphatase, aPTT, INR, and total bilirubin

The following analyses will be presented for the primary laboratory tests:

- descriptive statistics at each planned assessment,
- frequency of patients with transitions in CTCAE grade from baseline to worst and last values during treatment, and
- frequency of patients with possible clinically significant abnormalities.

Possible clinically significant abnormalities are defined as CTCAE grade of 2 or greater, with an increase of at least one grade from baseline.

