#### **4. CHANGES IN THE PLANNED ANALYSIS OF THE STUDY**

The protocol was amended to modify the futility analysis criterion to assess ORR as well as PFS6. This amendment is reflected in Sections [7.4](#) and [7.5.1](#) of this document.

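### The SAP's primary laboratory list departs from the protocol without saying so, and does not provide for on-treatment CTCAE tables for neutrophils and magnesium

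*SAP*

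**What the plan says.** Protocol 7.3.4 (Safety analyses) defines the primary laboratory tests in two directions. Ten tests are watched for a fall: "Low values (-): haemoglobin, total WBC, platelets, neutrophils, lymphocytes, potassium, magnesium, sodium, creatinine clearance and GFR". Six more are watched for a rise: "High values (+): AST, ALT, alkaline phosphatase, aPTT, INR, and total bilirubin". For these tests it promises three outputs:

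- a descriptive summary for every scheduled assessment;
- a grade-shift table, described as "frequency of patients with transitions in CTCAE grade from baseline to worst and last values during treatment";
- an abnormality count, described as "frequency of patients with possible clinically significant abnormalities", meaning a grade of 2 or more that is at least one grade worse than at baseline.

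Protocol 5.3.3 (Safety laboratory parameters) includes the white-cell differential with neutrophils, magnesium among the electrolytes, and creatinine clearance among the renal parameters. It introduces the table with "Following parameters should be evaluated at each timepoint".

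SAP 7.8.2 (Laboratory data) specifies the same three outputs for primary tests, with the same definition of an abnormality, but sets out its own list. The low-value list begins with RBC, haemoglobin, WBC and platelets and continues "neutrophils (only at baseline), lymphocytes, sodium, potassium, calcium, and glomerular filtration rate (GFR"). The high-value list has the protocol's six tests plus creatinine, LDH and uric acid. A closing note says that the parameters in protocol 5.3.3 will be summarised as well, without saying how.

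SAP Section 4 (Changes in the planned analysis) records one change: "The protocol was amended to modify the futility analysis criterion to assess ORR as well as PFS6".

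**The concern.** The SAP states in its introduction that it is based on the analyses in protocol Section 7. A reader would therefore expect the protocol's primary laboratory tests to carry through, or any difference to be declared. Three do not carry through as written, and no reason is given.

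At stake is systematic grading of measured values on treatment. In an uncontrolled trial, each patient's change from baseline is the main internal reference for laboratory toxicity. The protocol itself treats these signals as relevant. Section 2.3 says severe diarrhoea may lead to dehydration, with or without renal insufficiency. The diarrhoea table in 4.2.3.1 refers to electrolyte imbalance and to patients who are also neutropenic. The data will be collected, so the gap lies only in what the SAP commits to tabulate, for up to 80 treated patients (70 in Cohort A, 10 in Cohort B).

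**Working it through.** No formula applies. The check compares the two lists item by item, then asks what each remaining SAP provision gives for the items lost.

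**Step 1. The lists side by side** (protocol 7.3.4 against SAP 7.8.2)

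| | Low | High | Total |
|---|---|---|---|
| Protocol | 10 | 6 | 16 |
| SAP | 10 | 9 | 19 |
| In both | 8 | 6 | 14 |
| Protocol only | 2 (magnesium, creatinine clearance) | 0 | 2 |
| SAP only | 2 (RBC, calcium) | 3 (creatinine, LDH, uric acid) | 5 |

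The totals reconcile: 14 + 2 = 16 and 14 + 5 = 19. One of the 14 shared tests, neutrophils, is limited to baseline in the SAP. So 14 − 1 = 13 of the protocol's 16 tests keep the full on-treatment analysis. The three that do not are all among the 10 low-value tests.

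**Step 2. Can a baseline-only test enter the SAP's own tables?** The transition table needs a baseline grade and a worst or last grade during treatment. The abnormality count needs a post-baseline grade of 2 or more and a rise of at least one grade. A baseline-only test has no post-baseline grade, so neither output can be formed. The SAP thus names neutrophils as a primary test and excludes the values its primary-test analyses require.

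**Step 3. Do the data exist?** Yes. Protocol 5.3.3 lists all three parameters for every safety-laboratory time point. The Flow Chart places those at screening, at Course 1 (two visits), at the first visit of each later course, and at end of treatment.

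**Step 4. What else in the SAP covers the three tests?**

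| Test | Other coverage | What remains unprovided |
|---|---|---|
| Neutrophils | Total WBC and lymphocytes stay primary; 5.3.3 note; AE tables | CTCAE transitions and abnormality counts on treatment |
| Magnesium | 5.3.3 note; AE tables | The same |
| Creatinine clearance | GFR stays (low); creatinine added (high); 5.3.3 note; AE tables; listing for renal insufficiency | A separate row only |

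**Step 5. Is the change declared?** No. SAP Section 4 mentions the futility criterion alone. Because that entry refers to the protocol amendment, the SAP was written against the amended protocol, whose log records an update to the safety analyses in 7.3.4. The SAP list cannot be explained as following an older protocol.

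**The case against.** The strongest reply is that the SAP plans more than its primary list suggests, and much of that reply stands. The closing note brings every 5.3.3 parameter into some summary. SAP 7.8.2 applies CTCAE grades to laboratory parameters generally, under company standards that are not public, and it does not say that the three outputs are for primary tests *only*. Under protocol 5.3.6, laboratory changes the investigator judges clinically relevant are recorded as adverse events, and SAP 7.8.1 tabulates those by highest CTCAE grade. Dehydration and renal insufficiency have their own listings. Neutropenia is not among the afatinib toxicities named in protocol 1.2 and 2.3. The SAP list is also longer overall, and the baseline qualifier may be a drafting slip.

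A reader might therefore infer too much from the mismatch, namely that the tables will certainly be missing and that nothing will be reported on treatment for neutrophils or magnesium. The documents do not support that. The note and the adverse event tables both give some coverage, and the unseen standards may give more.

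The reply does not remove the point, for three reasons. The note leaves the type of summary open, while the transition and abnormality tables are specified for the primary list. For neutrophils, a general note sits against an explicit restriction to baseline. And adverse events that depend on an investigator's judgement of relevance are not the same information as grading every measured value.

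**Conclusion.** The point holds as an undeclared difference between protocol and SAP, together with an internal inconsistency in the SAP on neutrophils. As written, the SAP does not provide for the on-treatment CTCAE-transition and abnormality tables that the protocol promises for neutrophils and magnesium. The loss for creatinine clearance is minor, because GFR and high creatinine largely cover it.

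In size, 3 of 16 protocol primary tests are affected, of which 2 matter in practice. All of this is descriptive safety reporting. Data collection, the primary endpoint, the error rate and the sample size are untouched.

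The conclusion rests on reading the SAP as the governing public text. It assumes that an unspecified summary does not by itself commit the sponsor to graded shift tables. If the company standards or the technical SAP already require such tables for all graded parameters, the defect is one of wording, and the correction is the same.

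**What to change.** In SAP 7.8.2:

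1. Delete the baseline-only qualifier after neutrophils.
2. Add magnesium to the low-value list.
3. Add creatinine clearance as well, or state that GFR stands in for it.
4. Keep the five tests the SAP added.
5. State which analyses the closing note on protocol 5.3.3 covers, in particular whether it includes CTCAE transitions and abnormality counts.

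If any restriction or omission is intended, declare and justify it in SAP Section 4. The list would then hold 19 + 2 = 21 tests, or 20 if GFR stands in for creatinine clearance. The cost is a few extra rows in tables already planned, with no new data collection.

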### **7.8.3 Vital signs**

Only descriptive statistics are planned for this section of the report.

